4.7 Safety Analysis

Safety will be assessed through summaries of adverse events (AEs) and laboratory evaluations. All safety analyses will be based on the safety population, as defined in [Section 4.2](#), and will be summarized for each treatment group. These summaries will be presented separately for each infection study. In addition, adverse events and laboratory evaluations, as available, for BV Gel and VVC Gel will also be summarized by combining subjects who received the same treatment regimen across the studies. For example, those receiving BV Gel in the BV study will be combined with those receiving BV Gel in the Mixed Infection Study.

4.8.1 Adverse Events

Adverse events will be coded by system organ class and preferred term using the current version of Medical Dictionary for Regulatory Activities (MedDRA). Each verbatim adverse event will be translated to a preferred term, a higher-level included term, and finally a system-organ class. Adverse events will be summarized by system organ class and preferred term, counting proportions of the patients who experienced at least one such adverse event. Frequencies of patients with treatment-emergent adverse events (TEAEs), sorted by system organ class, will be summarized by treatment group. TEAEs are defined as those AEs that develop or worsen after the first dose of study medication.

A secondary analysis of TEAEs judged by the Investigator to be related to study drug will be performed. This analysis will be summarized identically to the above analysis. Additional breakdowns of serious adverse events (SAEs) and treatment related SAEs will be summarized and described in a similar fashion.

Summaries of AE durations, severity, relatedness to study drug, counter measures taken, and outcome will also be produced as warranted. At the least, incidence of drug discontinuation and death will be summarized.

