1.2 Study Design

This is a multi-center, phase III trial, comprised of three studies, each designed to test the safety and efficacy of a different investigational product, for a specific vaginal infection/indication. They are:

1. Bacterial Vaginosis (BV) Study: A randomized, double-blind, parallel-group, placebo-controlled study to test the safety and efficacy of BV Gel (0.9% metronidazole gel) for the treatment of BV
2. Vulvovaginal Candidiasis (VVC) Study: A randomized, double-blind, parallel-group, placebo-controlled study to test the safety and efficacy of VVC Gel (0.8% terconazole gel) for the treatment of VVC
3. Mixed Infection (Concurrent BV and VVC) Study: A randomized, double-blind, parallel-group, active-controlled study to test the safety and efficacy of Combo Gel (0.9% metronidazole gel and 0.8% terconazole gel) for the treatment of Mixed Infection

All study medication is intravaginal and will be dosed as one applicator for three consecutive days. Subjects who sign an informed consent form (ICF), are diagnosed with BV, VVC, or Mixed Infection, and meet eligibility requirements will be enrolled into the appropriate infection study and subsequently

randomized to treatment based on clinical diagnosis at the screening and enrollment/baseline visit (Visit 1). BV subjects will be entered into the BV Study, VVC subjects will be entered into the VVC Study, and concurrent BV and VVC (Mixed Infection) subjects will be entered into the Mixed Infection Study.

All subjects will be asked to return for a test of cure visit (Visit 2) 7-14 days after randomization. If a subject is menstruating on the day of the scheduled visit, she should be rescheduled to return 24 hours after completion of menses. Subjects who in the opinion of the investigator/clinician require additional treatment for vaginal discomfort/symptoms and subjects who self-medicated for vaginal discomfort/symptoms, will be terminated from the study. All other subjects will return for a follow-up evaluation visit (Visit 3) 21-30 days after randomization.

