3. STUDY OBSERVATIONS

The evaluation of subject eligibility will occur at the Baseline visit (visit 1). Eligible subjects will receive a maximum duration of treatment of three days and a maximum trial duration of 30 days from the time of randomization. The test of cure visit (visit 2) will occur 7-14 days after randomization. If the subject did not need additional treatment for vaginal discomfort/symptoms (and the subject did not self-medicate), the subject will be asked to return 21-30 days after randomization (visit 3).

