3.2 Test of Cure Visit (Visit 2) Evaluations

The procedures listed below will be performed 7-14 days after randomization for the purpose of determining subject compliance/evaluability with drug administration and study instructions, evaluating the subject's response to therapy and whether or not additional treatment is needed (i.e. cure or failure), and obtaining information on concomitant medication use and possible adverse events.

- Review of Diary
- Assessment of Compliance: Subjects are queried to determine compliance with study drug administration and study instructions.
- Time to Symptom Resolution/Reoccurrence: Symptom resolution and reoccurrence will be assessed by review of the subject's diary and subject interview. Dates of symptom resolution and/or symptom recurrence should be documented.
- Subject Assessment of Symptoms: Subjects will be asked to rate their current vulvovaginal symptoms of itching, burning, and irritation as absent=0, mild=1, moderate=2, or severe=3. The sum of this symptom score will be added to the vulvovaginal signs score obtained during the pelvic examination to determine a combined symptom and sign severity score.
- Laboratory Tests and Specimen Collections: The lab tests listed below will be obtained at Visit 2.

- CBC with differential and blood chemistries (i.e. BUN, Creatinine, ALT, AST, ALP, and bilirubin) only for subjects enrolled in the Mixed Infection Study
- Vaginal culture for Candida species
- Vaginal Gram stain
- Pelvic Examination and Specimen Collections
 - Vulvovaginal signs rating
 - Vaginal discharge characterization
 - Vaginal pH measurement
 - KOH Whiff Test
 - Saline wet mount
 - Vaginal Candida culture
 - Vaginal Gram stain
- Assessment of Clinical Status, Need for Additional Treatment: Following subject evaluation, the investigator/clinician will be asked to document whether the subject requires any additional treatment for vaginal discomfort/symptoms. Subjects who do require additional treatment should be treated per investigator/clinician judgment and terminated from the study. Subjects who do not require treatment (and subjects who did not self-medicate) may remain in the study and return for their regularly scheduled follow up visit (Visit 3).
- Determination of Cure or Failure of Subject's Enrolled Infection:
 - BV subjects must satisfy all three of the clinical criteria listed below in order to be considered a BV cure (i.e. clinical cure).
 - Discharge has returned to normal/physiologic¹

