3.4 Limited Termination Visit

In instances where Visit 1 lab results make a subject ineligible for the study (i.e. subject randomized but did not meet inclusion/exclusion criteria), subjects should be terminated when exclusionary lab results become known. Procedures for these subjects are more limited but require a safety assessment including collection of adverse events, concomitant medications, and safety blood labs if the subject was enrolled in the Mixed Infection Study and safety labs were not already obtained at Visit 2. Subject diaries should be reviewed and unused drug tubes collected. Drug administration/compliance should be ascertained if not already done. Lab results that would make a subject ineligible are: positive gonorrhea, chlamydia, trichomonas, or herpes tests; normal Nugent score < 4 (for BV and Mixed Infection subjects); or negative *Candida* culture (for VVC and Mixed Infection subjects).

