4.7.2 Secondary Efficacy Analyses

Secondary efficacy endpoints are listed in [Section 4.3](#). These endpoints include variables that are categorical (including binary variables), ordinal (such as rating scores), or time to event variables (such as time to resolution of symptoms). The analysis of the secondary endpoints will be performed using the mITT population with worst case scenario imputation for missing data, with supportive analyses conducted using the PP population.

For the secondary endpoints that are categorical or ordinal with four or fewer levels (including binary outcome variables), the analysis will include the proportion of subjects with each criteria or each score, at baseline and endstudy. The comparison of treatment groups will be performed using Chi-squared tests if all expected cell counts are at least 5, and Fisher's Exact test otherwise. For binary outcomes, (clinical outcome, mycological outcome, and eradication [or persistence] of individual fungal species) 95% two-sided confidence intervals for the difference in proportions will also be constructed using the continuity corrected Wald intervals when Chi-square tests are appropriate, or the method of Chan and Zhang (1999) otherwise.

Secondary endpoints that are ordinal data with more than four levels, such as Nugent score, the median score at baseline, endstudy, and the change from baseline will be computed, in addition to the proportion of subjects at each level. Treatment comparisons will be performed using the Wilcoxon Rank Sum test.

The secondary endpoint of time to resolution of symptoms will be analyzed in each infection study by arm using log-rank tests to compare arms within each study and Kaplan-Meier plots. Kaplan-Meier estimates of the quartiles for time to resolution will be computed, along with 95% confidence intervals. Censoring times for the Kaplan-Meier estimates will be based on the date of last contact or visit 3 (whichever is earliest) if symptoms never resolved or the patient was an early withdrawal and status is unknown.

The analysis of eradication (persistence) of individual fungal species will be conducted in subgroups of subjects defined by fungal species present at baseline (for the VVC and Mixed Infection studies).

In addition, for each study a summary will be made of subjects classified as:

- Persistent Infection – no cure at Visit 2 or Visit 3
- Persistent Cure – cure at Visit 2 and Visit 3
- Late Cure – no cure at Visit 2 but cure at Visit 3

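### TEAE incidence is compared by crude proportions although length of AE follow-up depends on response, so the more effective arm may show more TEAEs with no drug effect

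*SAP*

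**What the plan says.** Section 4.8.1 counts subjects with at least one event, "counting proportions of the patients who experienced at least one such adverse event", by treatment group. The window has a start but no stated end: "TEAEs are defined as those AEs that develop or worsen after the first dose of study medication".

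Time under observation is set elsewhere. Section 1.2: "All subjects will be asked to return for a test of cure visit (Visit 2) 7-14 days after randomization". Section 3.2, on that visit: "Subjects who do require additional treatment should be treated per investigator/clinician judgment and terminated from the study". Section 1.2 applies the same rule to subjects who self-medicated, and then says "All other subjects will return for a follow-up evaluation visit (Visit 3) 21-30 days after randomization". AE information is collected at both visits (Sections 3.2 and 3.3). Section 3 gives "a maximum duration of treatment of three days and a maximum trial duration of 30 days", which caps follow-up but does not equalise it.

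Not every non-cure leaves at Visit 2. Section 4.7.2 has a Late Cure category, "no cure at Visit 2 but cure at Visit 3", which requires some non-cures to remain on study.

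The table list in Section 14.3 includes drug exposure and compliance, but no time on study, no rate per unit of time and no TEAE table by period.

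**The concern.** Under these rules a subject's response to treatment helps decide whether AEs are collected for roughly one and a half weeks or for three to four. Section 4.5 expects large differences in response between arms. The arm with more cures should then have more subject-days in which an AE can be recorded, and a crude proportion makes no allowance for that. For time to resolution of symptoms, Section 4.7.2 defines censoring; AEs get no comparable handling.

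Safety is part of each primary objective (Section 1.1). The BV and VVC studies take no safety laboratory samples after baseline, so the AE tables carry most of the comparative safety evidence there. As planned, they would not let a reader separate a drug effect from longer observation.

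**Working it through.** **Inputs from the SAP.** Expected cure rates (Section 4.5): BV study 0.50 vs 0.20; VVC study 0.70 vs 0.20; Mixed study 0.35 vs 0.10. Visit windows: day 7-14 and day 21-30.

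**Check of the plan's own figures.** The safety section states no number, so the check is on the sample-size table that supplies the cure rates. Exact power of the two-sided 0.05 Fisher test is 90.6% (58 per arm), 99.94% (50 per arm) and 90.6% (63 per arm), against the stated 90.0%, > 99.9% and 90%. The total is 2×58 + 2×50 + 3×63 = 405. These agree.

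**Assumptions, not in the SAP.** Visits fall at the midpoints, day 10.5 and day 25.5. A share *s* of non-cures is terminated at Visit 2, the same in both arms. AE risk over time is the same in both arms and in cured and uncured subjects.

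**Mean follow-up.** With cure rate *p*, the fraction leaving at Visit 2 is t = s(1 − p), and mean follow-up is 10.5t + 25.5(1 − t) days.

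| Study | s = 1 | ratio | s = 0.5 | ratio |
|---|---|---|---|---|
| BV | 18.0 vs 13.5 | 1.33 | 21.75 vs 19.5 | 1.12 |
| VVC | 21.0 vs 13.5 | 1.56 | 23.25 vs 19.5 | 1.19 |
| Mixed | 15.75 vs 12.0 | 1.31 | 20.63 vs 18.75 | 1.10 |

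For example, BV Gel at s = 1 gives 0.5×10.5 + 0.5×25.5 = 18.0. Over the extremes of the visit windows, the s = 1 ratios run from 1.12 to 1.99.

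**Effect on crude incidence.** Let R2 and R3 be the risk of at least one TEAE by Visit 2 and by Visit 3. Incidence in an arm is t·R2 + (1 − t)·R3, so the difference between arms with no drug effect is s × (difference in cure rates) × (R3 − R2).

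*Constant hazard, 10% by day 10.5.* R3 = 1 − 0.9^(25.5/10.5) = 22.6%, so R3 − R2 = 12.6 points. At s = 1:
- BV: 16.3% vs 12.5%, difference 0.30×12.6 = 3.8 points
- VVC: 18.8% vs 12.5%, difference 0.50×12.6 = 6.3 points
- Mixed: 14.4% vs 11.3%, difference 0.25×12.6 = 3.1 points (3.15 before rounding down)

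The difference is proportional to *s*. Incidence ratios are about 1.11, 1.18 and 1.09 at s = 0.5, and 1.05, 1.08 and 1.04 at s = 0.25.

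*AEs concentrated early, 20% overall risk.* If 25% of AEs arise after Visit 2, R3 − R2 = 5 points and the differences at s = 1 are 1.5, 2.5 and 1.25 points. If 10% do, R3 − R2 = 2 points and they are 0.6, 1.0 and 0.5 points.

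**With a common window to Visit 2.** Every arm has expected incidence R2 (10% in the constant-hazard case), so the artificial difference is zero, provided Visit 2 falls on similar days in each arm.

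**The case against.** The strongest reply is that the effect may be small. Dosing lasts three days, so AEs may cluster well before Visit 2. Cure is strictly defined, so many non-cures may need no treatment and stay to Visit 3. The SAP plans no AE hypothesis test and no decision rule, and disposition by arm with reasons for withdrawal (Section 4.4, Table 14.1.1) will show differential exit. Even the upper-bound BV gap, 16.3% vs 12.5% with 58 per arm, is about 0.6 standard errors. AE follow-up after termination may also be set in the protocol, which is not at hand. All of this stands and limits the size. It does not make the crude comparison sound, because disposition counts do not show AE follow-up time and the planned tables could not tell a reader which case occurred.

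Four stronger readings are tempting, and the SAP does not support them:
- *All failures leave at Visit 2.* The Late Cure category contradicts this, so the s = 1 figures are an upper bound.
- *The more effective arm will look less safe.* That needs a material AE rate between the visits, which the SAP does not give.
- *Early exit of laboratory-ineligible subjects adds to the bias.* Section 3.4 says "subjects should be terminated when exclusionary lab results become known", but those results come from Visit 1. The exits do not depend on response, and randomisation balances them in expectation.
- *The combined-study tables are biased in the same direction.* BV Gel and VVC Gel are each the longer-followed arm in their own study and a shorter-followed arm in the Mixed study. At s = 1, pooled BV Gel mixes means of 18.0 and 12.0 days. No pooled placebo comparison is specified, so no direction follows.

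**Conclusion.** The concern holds in a limited form. Length of AE collection depends on response, the between-arm summary ignores this, and nothing planned corrects or displays it. On the expected cure rates the likely direction is longer follow-up on BV Gel, VVC Gel and Combo Gel than on their comparators within each study.

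With midpoint visits and equal risk, the artificial difference ranges from about 1 point or less, if only a tenth of AEs arise after Visit 2, to about 3 to 6 points as an upper bound, if every non-cure is terminated and the hazard is constant with 10% incidence by day 10.5. The share of non-cures terminated, the timing of AEs and the actual visit days are assumptions. The consequence is for reading the safety tables, not for type I error. The point is worth acting on because the remedy is cheap.

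**What to change.** In Section 4.8.1, add a by-arm table of TEAEs with onset from first dose to each subject's Visit 2, or to the last AE assessment if earlier, and name it as the between-arm comparison within each study. State how a dosed subject who missed Visit 2 but attended Visit 3 is handled, since Sections 1.2 and 3.3 allow for this. A fixed day-14 cut would not serve: a subject terminated on day 7 would contribute 7 days and a continuing subject 14.

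Report time on study in subject-days by arm beside the all-period TEAE tables (14.3.3 to 14.3.7) and the combined-study tables (14.3.12 to 14.3.16). Keep the all-period tables. Any table of TEAEs after Visit 2 among continuing subjects should be labelled descriptive only, because its denominator is selected by response.

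The change needs no alteration to the termination rules or to data collection; it uses visit and AE onset dates, and Section 4.6 already has rules for missing AE start dates. The cost is SAP wording and one or two extra outputs.

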4.8.2 Laboratory Assessments

CBC with differential and blood chemistry data will be collected in the Mixed Infection study only. Values will be tabulated and compared to baseline for the Mixed Infection study population. Laboratory endpoints will be summarized for baseline, endstudy, and for change from baseline to endstudy using descriptive statistics (mean, median, standard error, minimum, and maximum). In addition, summarization of laboratory values that deviate substantially from the normal reference range will be provided. The reference ranges for normal laboratory values will be provided by the central laboratory.

A shift table will be provided, which will tabulate the proportion of subjects in each treatment group who change from low abnormal (< LLN), normal, or high abnormal (> ULN) at baseline to low abnormal, normal, or high abnormal at Visit 2, as shown in the following table.

Mixed Infection Study

Endpoint	Treatment	Baseline	Visit 2/EndStudy		
			Low (L)	Normal (N)	High (H)
BUN	BV Gel	Low (L)	xx	xx	xx
		Normal (N)	xx	xx	xx
		High (H)	xx	xx	xx
		n	xxx		
	VVC Gel				
			Low (L)	Normal (N)	High (H)
		Low (L)	xx	xx	xx
		Normal (N)	xx	xx	xx
		High (H)	xx	xx	xx
	n	xxx			
	Combo Gel				
			Low (L)	Normal (N)	High (H)
		Low (L)	xx	xx	xx
		Normal (N)	xx	xx	xx
		High (H)	xx	xx	xx
n	xxx				
etc		n	xxx		

All laboratory data will be provided in listings. Abnormal laboratory values, defined as observations outside the normal range, will be flagged in the listing.

4.8.3 Vital Signs

Vital signs are only collected before administration of study drug and will be summarized within each infection study pooling treatment groups. Vital sign data will also be presented in listings.

4.8.4 Physical Exams

All physical exam data will be presented in listings.

14. LIST OF TABLES, FIGURES, AND LISTINGS

LIST OF TABLES AND FIGURES

14.1 Demographic and Study Conduct Summaries

Table 14.1.1	Summary of Subject Disposition, All Randomized Subjects
Table 14.1.2	Summary of Subject Accounting, All Randomized Subjects
Table 14.1.3	Summary of Major Protocol Violations, All Randomized Subjects
Table 14.1.4	Summary of Inclusion/Exclusion Criteria Not Met, All Randomized Subjects
Table 14.1.5	Summary of Demographic and Baseline Characteristics, mITT Population
Table 14.1.6	Summary of Contraceptive and Obstetric Status, mITT Population
Table 14.1.7	Summary of History of Gynecologic Infection, mITT Population
Table 14.1.8	Summary of Infection Medications, mITT Population
Table 14.1.9	Summary of Past Medical and Surgical History, mITT Population
Table 14.1.10	Summary of Current Medical and Surgical History, mITT Population
Table 14.1.11	Summary of Baseline Vital Signs, mITT Population
Table 14.1.12	Summary of Baseline Physical Exam, mITT Population
Table 14.1.13	Summary of Baseline Symptom and Sign Severity Score, mITT Population
Table 14.1.14	Summary of Baseline Pelvic Exam, mITT Population

14.2 Efficacy Summaries

Table 14.2.1.1	Summary of Primary Endpoint for BV Study – Test-of-Cure, mITT Population
Table 14.2.1.2	Summary of Primary Endpoint for BV Study – Test-of-Cure, PP Population
Table 14.2.2.1	Summary of Primary Endpoint for VVC Study – Test-of-Cure, mITT Population
Table 14.2.2.2	Summary of Primary Endpoint for VVC Study – Test-of-Cure, PP Population
Table 14.2.3.1	Summary of Primary Endpoint for Mixed Infection Study – Test-of-Cure, mITT Population
Table 14.2.3.2	Summary of Primary Endpoint for Mixed Infection Study – Test-of-Cure, PP Population
Table 14.2.4	Exploratory Analysis of Primary Endpoint by Month of Study, For Patients Receiving BV Gel – Test-of-Cure, mITT Population
Figure 14.2.5	Time Plot of Primary Endpoint by Month of Study, For Patients Receiving BV Gel – Test-of-Cure, mITT Population
Table 14.2.6	Summary of Visit 2 Symptom and Sign Severity Score, mITT Population
Table 14.2.7	Summary of Visit 2 Pelvic Exam, mITT Population
Table 14.2.8	Summary of Visit 2 Compliance Assessment, mITT Population
Table 14.2.9	Summary of Visit 2 Need for Additional Treatment, mITT Population
Table 14.2.10.1	Summary of Visit 2 BV Clinical Cure, mITT Population
Table 14.2.10.2	Summary of Visit 2 BV Clinical Cure, PP Population
Table 14.2.11.1	Summary of Visit 2 VVC Clinical Cure, mITT Population
Table 14.2.11.2	Summary of Visit 2 VVC Clinical Cure, PP Population
Table 14.2.12.1	Summary of Visit 2 Gram Stain Cure, mITT Population
Table 14.2.12.2	Summary of Visit 2 Gram Stain Cure, PP Population
Table 14.2.13.1	Summary of Visit 2 Candida Culture Cure, mITT Population
Table 14.2.13.2	Summary of Visit 2 Candida Culture Cure, PP Population
Table 14.2.14.1	Summary of Visit 2 Combined BV Clinical and Gram Stain Cure, mITT Population
Table 14.2.14.2	Summary of Visit 2 Combined BV Clinical and Gram Stain Cure, PP Population
Table 14.2.15.1	Summary of Visit 2 VVC Clinical and Candida Culture Cure, mITT Population
Table 14.2.15.2	Summary of Visit 2 VVC Clinical and Candida Culture Cure, PP Population

Table 14.2.16	Summary of Visit 2 Change in Pelvic Exam Results, mITT Population
Table 14.2.17	Summary of Visit 2 Change in Signs and Symptoms, mITT Population
Table 14.2.18	Summary of Visit 2 Eradication/Persistence of Candida Species, mITT Population
Table 14.2.19	Summary of Time to Resolution of Symptoms, mITT Population
Figure 14.2.20	Kaplan-Meier Curve of Time to Resolution of Symptoms
Table 14.2.21.1	Summary of Shifts in Cure Status From Visit 2 to Visit 3, mITT Population
Table 14.2.21.2	Summary of Shifts in Cure Status From Visit 2 to Visit 3, PP Population

